7.0 Study Objectives

7.1 Primary Objective

The primary objective of this study is to evaluate the safety and efficacy of pitolisant compared with placebo in treating excessive daytime sleepiness (EDS) in patients with Prader-Willi syndrome (PWS) ages 6 to 65 years.

7.2 Secondary Objectives

Key Secondary Objectives

The key secondary objectives of this study are to evaluate the following in patients with PWS ages 6 to 65 years treated with pitolisant compared with placebo:

- Caregiver-rated impressions of severity of EDS
- Clinician-rated impressions of severity of overall clinical status

Other Secondary Objectives

Other secondary objectives of this study are to evaluate the following in patients with PWS ages 6 to 65 years:

- The impact of pitolisant on behavioral symptoms
- The impact of pitolisant on cognitive function
- Change in caregiver burden
- Safety and effectiveness of pitolisant during long-term treatment

7.3 Exploratory Objectives

The exploratory objectives of this study are to evaluate the following in patients with PWS ages 6 to 65 years:

- The impact of pitolisant on hyperphagia
- The impact of pitolisant on changes in plasma ghrelin levels
- The PK of pitolisant and its major metabolite, BP1.3484
- The relationship between plasma levels of pitolisant (PK) and treatment effect (pharmacodynamics)

8.0 Study Design

8.1 General Design

This is a randomized, double-blind, placebo-controlled, parallel group, Phase 2 proof of concept study in patients (ages 6 to 65 years) with PWS, followed by an optional OLE Phase.

The study will consist of a Screening Period (up to a maximum of 45 days), an 11-week Double-Blind Treatment Phase (including a 3-week Titration Period and an 8-week Stable Dose

Period), and an optional OLE Phase. The OLE Phase is expected to be multi-year in duration. An overall schema of the study design is provided in Figure 1.

During Screening, patients who meet all eligibility criteria will be randomized in a 1:1:1 ratio to receive treatment with low dose pitolisant, high dose pitolisant, or matching placebo (approximately patients per treatment group, ages 6 to 65 years). The low and high pitolisant doses, respectively in each age group, will be 8.9 mg and 17.8 mg for children ages 6 to <12 years, 13.35 mg and 26.7 mg for adolescents ages 12 to <18 years, and 17.8 mg and 35.6 mg for adults ages 18 to 65 years.

[figure not shown]
The day after the Baseline Visit, patients will take their first dose of study drug. In the Double-Blind Treatment Phase, patients will be titrated to their randomized stable dose of study drug during the 3-week Titration Period; study drug dose will be titrated on Day 8 and again on Day 15 (based on randomized stable dose, per Table 1, with all patients at their randomized stable dose by Day 15). After completion of the 3-week Titration Period, patients will continue to take study drug at their randomized stable dose for an additional 8 weeks of blinded treatment (Stable Dose Period; Days 22 to 77). The duration of the Double-Blind Treatment Phase will be 11 weeks.

Adjustments to study drug dosing outside the protocol-specified titration schedule are not permitted during the 11-week Double-Blind Treatment Phase of the study.

Eligible patients who complete the Double-Blind Treatment Phase will be given the opportunity to participate in an optional OLE Phase. During the OLE Phase, all eligible patients will complete titration during a 3-week Titration Period to a maximum target dose based on their age (17.8 mg for ages 6 to <12 years, 26.7 mg for ages 12 to <18 years, or 35.6 mg for ages 18 to 65 years; Table 2). At the end of the 3-week Titration Period, patients will continue to take their target dose of pitolisant once daily in the morning upon wakening until the end of the study. Adjustments to pitolisant dose are permitted during the OLE Phase; pitolisant dose can be adjusted (higher or lower) based on Investigator assessment of clinical response, tolerability, and/or patient age. The maximum doses allowed in the study are 17.8 mg for children 6 to <12 years, 26.7 mg for adolescents 12 to <18 years, and 35.6 mg for adults 18 to 65 years.

The Coronavirus Disease 2019 (COVID-19) pandemic has had a major impact on the conduct of clinical trials worldwide, including restrictions on travel, dislocation of clinical trial patients, and the need of many health care facilities to handle an influx of patients with COVID-19. Recognizing the impact of COVID-19 on clinical trials, the National Institutes of Health (NIH) and the U.S. Food and Drug Administration (FDA) released guidance to provide general considerations to assist sponsors in assuring the safety of trial participants, maintaining compliance with good clinical practice (GCP), and minimizing risks to trial integrity for the duration of the COVID-19 public health emergency. Details of analyses of data collected regarding the impact of COVID-19 on this study are included in applicable sections throughout.

Abbreviations: AE = adverse event; EOT = End of Treatment; F-Up = follow-up; OLE = Open Label Extension; PK = pharmacokinetics; TC = telephone call; V = Visit.

^a The Titration Period for the Double-Blind Treatment Phase will be from Days 1 to 21. Patients will receive their first dose of study drug on Day 1; study drug dose will be titrated on Day 8 and again on Day 15 (as appropriate based on randomized stable dose); all patients will be at their randomized stable dose by Day 15 of the Titration Period.

^b The 8-week Stable Dose Period for the Double-Blind Treatment Phase will be from Days 22 to 77 (±3 days); patients will take their last dose of blinded treatment on Day 77 (±3 days). Visit 5 (Day 77 ±3 days) is the EOT Visit for the Double-Blind Treatment Phase. Eligible patients who opt to enter the OLE Phase will be dispensed open-label pitolisant at this visit.

^c The Titration Period for the OLE Phase will be from Days 78 to 98 (±3 days). Eligible patients will receive their first dose of open-label pitolisant on Day 78 and pitolisant dose will be titrated on Day 85 and again on Day 92 to the target dose. At the end of the 3-week Titration Period, patients will continue to take their target dose of pitolisant once daily in the morning upon wakening until the end of the study (Long-term Dosing Period). During the OLE Phase, pitolisant dose can be adjusted (higher or lower) based on Investigator assessment of clinical response, tolerability and/or patient age; the maximum doses allowed in the study are 17.8 mg for children 6 to <12 years, 26.7 mg for adolescents 12 to <18 years, and 35.6 mg for adults 18 to 65 years.

d All AEs regardless of seriousness, severity, or causality will be collected from the time the patient/parent(s)/legal guardian(s) provides written informed consent/assent through 30 days (+3 days) after final dose of study drug (Safety Follow-up TCs). At the Safety Follow-up TCs, AEs (including inquiries regarding

signs and symptoms of arrhythmia, any other cardiac manifestations [e.g., syncope], and psychiatric events [e.g., suicidality, compulsive behavior, anxiety]) and concomitant medication use will be recorded.

During the first year of the OLE Phase of the study, patients will have the option to complete up to two of the scheduled on-site study visits remotely (i.e., two of Visits 6, 7, 8, and 9); thereafter (i.e., after Visit 9/Month 12), patients will have the option to complete one of the two scheduled on-site study visits remotely per year.

Table 1: Study Drug Dosing in the Double-Blind Treatment Phase, Once Daily

	Titration Period ^a (3 Weeks)			Stable Dose Period ^b (8 Weeks)	
Age/Treatment Groups	Week 1 (Days 1 – 7)	Week 2 (Days 8 – 14)	Week 3 (Days 15 – 21)	Weeks 4 – 11 (Days 22 – 77)	
Pediatric patients (6 to <	(12 years)				
Low dose pitolisant	4.45 mg	8.9 mg	8.9 mg	8.9 mg	
High dose pitolisant	4.45 mg	8.9 mg	17.8 mg	17.8 mg	
Placebo	Matching tablets	Matching tablets	Matching tablets	Matching tablets	
Adolescent patients (12 t	o <18 years)				
Low dose pitolisant	4.45 mg	8.9 mg	13.35 mg	13.35 mg	
High dose pitolisant	8.9 mg	17.8 mg	26.70 mg	26.70 mg	
Placebo	Matching tablets	Matching tablets	Matching tablets	Matching tablets	
Adult patients (18 to 65 years)					
Low dose pitolisant	4.45 mg	8.9 mg	17.8 mg	17.8 mg	
High dose pitolisant	8.9 mg	17.8 mg	35.6 mg	35.6 mg	
Placebo	Matching tablets	Matching tablets	Matching tablets	Matching tablets	

a Study drug dose will be titrated on Day 8 and again on Day 15 (as appropriate based on randomized stable dose); all patients will be at their randomized stable dose by Day 15.

Table 2: Pitolisant Dosing in the Open-Label Extension Phase, Once Daily

	Titration Period ^a (3 Weeks)			Long-Term Dosing Period ^b
Age Groups	Week 12 Days 78-84	Week 13 Days 85-91	Week 14 Days 92-98	Week 15 (Day 99) to EOT
Pediatric patients (6 to <12 years)	4.45 mg	8.9 mg	17.8 mg	17.8 mg
Adolescent patients (12 to <18 years)	8.9 mg	17.8 mg	26.7 mg	26.7 mg
Adult patients (18 to 65 years)	8.9 mg	17.8 mg	35.6 mg	35.6 mg

Abbreviations: EOT = End of Treatment; OLE = Open-Label Extension

Note: Adjustments to pitolisant dose are permitted during the OLE Phase. Pitolisant dose can be adjusted (higher or lower) based on Investigator assessment of clinical response, tolerability and/or patient age; the maximum doses allowed in the study are 17.8 mg for children 6 to <12 years, 26.7 mg for adolescents 12 to <18 years, and 35.6 mg for adults 18 to 65 years.

b Study drug doses for the Stable Dose Period; dose adjustments outside the protocol-specified titration schedule are not permitted in the Double-Blind Treatment Phase.

^a Pitolisant dose will be titrated on Day 85 and again on Day 92.

b After completion of the 3-week Titration Period, patients will continue to receive pitolisant at a target dose of 17.8 mg (ages 6 to <12 years), 26.7 mg (ages 12 to <18 years), 35.6 mg (ages 18 to 65 years), unless they were not titrated to the target dose and are receiving a lower dose based on clinical response and/or tolerability.

8.2 Sample Size Considerations

The planned sample size is patients (in the low dose pitolisant group, in the high dose pitolisant group, and in the placebo group). Prior research suggests that the Epworth Sleepiness Scale for Children and Adolescents (ESS-CHAD) standard deviation (SD) falls between 5 to 6; at the lower end of this range, the study would be powered at to detect a difference of between the pooled pitolisant dosage groups and placebo group. However, as a proof-of-concept study, statistical separation is not a strict objective of the trial, especially with regard to the individual dosage groups versus placebo. The proposed sample size will yield a 95% confidence interval of with an SD of and with an SD of ; this will give sufficient precision to inform future studies.

8.3 Randomization

Eligible patients will be randomly assigned in a 1:1:1 ratio via an interactive voice/web response system (IXRS) to low dose pitolisant, high dose pitolisant, or matching placebo.

Enrolled patients will be allocated a unique patient number in a sequential order by trial site. Following randomization, Harmony Biosciences will provide all study drug in a packed and labeled kit, and the IXRS will identify the kit number to be dispensed to the patient at each relevant visit according to the treatment assigned in the randomization schedule.

9.0 Study Endpoints, Conventions and Derivations

9.1 Endpoints

Table 3 and Table 4 list the objectives and the assessments being used for the respective endpoints in the study.

Table 3: Double-Blind Treatment Phase Objectives and Endpoints

DOUBLE-BLIND TREATMENT PHASE			
Primary Objective	Primary Endpoint		
To evaluate the safety and efficacy of pitolisant compared with placebo in treating EDS in patients with PWS ages 6 to 65 years.	Change in mean ESS-CHAD (parent/caregiver version) score from Baseline to Week 11 (Visit 5) for pitolisant compared with placebo		
Key Secondary Objectives	Key Secondary Endpoints		
To evaluate caregiver-rated impressions of severity of EDS and clinician-rated impressions of severity of overall clinical status in patients with PWS ages 6 to 65 years treated with pitolisant compared with placebo.	Change from Baseline to Week 11 (Visit 5) for pitolisant compared with placebo in: • Caregiver Global Impression of Severity (CaGI-S) for EDS • Clinical Global Impression of Severity (CGI-S) for overall clinical status related to PWS		

Other Secondary Objectives	Other Secondary Endpoints
To evaluate the following in patients with PWS ages 6 to 65 years:	Change from Baseline to Week 11 (Visit 5) for pitolisant compared with placebo in:
 The impact of pitolisant on behavioral symptoms The impact of pitolisant on cognitive function Change in caregiver burden 	 Behavior as measured by the Aberrant Behavior Checklist, Second Edition (ABC-2) Behavioral and cognitive rigidity as measured by the Montefiore-Einstein Rigidity Scale – Prader-Willi Syndrome (MERS-PWS) Psychomotor function as measured by the Cogstate Detection test Attention as measured by the Cogstate Identification test Working memory as measured by the Cogstate One Back test Measure of caregiver burden using the 22-item Zarit Burden Interview (ZBI-22)
Exploratory Objectives	Exploratory Endpoints
To evaluate the following in patients with PWS ages 6 to 65 years: • The impact of pitolisant on hyperphagia • The impact of pitolisant on changes in ghrelin levels • The PK of pitolisant and its major metabolite, BP1.3484 • The relationship between plasma levels of pitolisant (PK) and treatment effect (PD)	Change from Baseline to Week 11 (Visit 5) for pitolisant compared with placebo in: • Total score of the Hyperphagia Questionnaire for Clinical Trials (HQ-CT) in conjunction with the Food Safe Zone Questionnaire (FSZQ) • Acylated and unacylated ghrelin levels PK endpoints for both pitolisant and its major metabolite, BP1.3484: • Maximum observed plasma concentration (C _{max}) • Area under the plasma concentration-time curve (AUC) from time 0 to the last collection time (AUC _{last}) after administration of pitolisant • Time to observed maximum plasma concentration (t _{max}) Exposure-response relationship between plasma
Safety	pitolisant levels and change in efficacy measures Safety Endpoints
To assess the safety and tolerability of pitolisant in patients with PWS ages 6 to 65 years	AEs Clinical laboratory results Vital signs 12-lead electrocardiogram (ECG) Suicidality: Columbia-Suicide Severity Rating Scale (C-SSRS)

	 Anxiety: Anxiety, Depression, and Mood Scale (ADAMS) Seizures Physical Examinations
--	---

Abbreviations: ABC-2 = Aberrant Behavior Checklist, Second Edition; ADAMS = Anxiety, Depression, and Mood Scale; AE = Adverse Event; AUC = Area under the plasma concentration-time curve; C-SSRS = Columbia-Suicide Severity Rating Scale; CAGI-S = Caregiver Global Impression of Severity; CGI-S = Clinical Global Impression of Severity; C_{max} = Maximum observed plasma concentration; ECG = electrocardiogram; EDS = Excessive Daytime Sleepiness; ESS-CHAD = Epworth Sleepiness Scale for Children and Adolescents; FSZQ = Food Safe Zone Questionnaire; HQ-CT = Hyperphagia Questionnaire for Clinical Trials; MERS- PWS = Montefiore-Einstein Rigidity Scale – Prader-Willi Syndrome; PK = Pharmacokinetic(s); PWS = Prader-Willi Syndrome; T_{max} = Time to observed maximum plasma concentration; ZBI-22 = 22-item Zarit Burden Interview.

Table 4: Open-Label Extension Phase Objectives and Endpoints

OPEN-LABEL EXTENSION			
Objectives	Efficacy Endpoints		
To evaluate the long-term effectiveness of pitolisant	During the patient's first year of participation, changes from Baseline in:		
	 ESS-CHAD as rated by caregivers/parents, CaGI-S for EDS CGI-S for overall clinical status related to PWS ABC-2 MERS-PWS Cogstate Detection test Cogstate Identification test Cogstate One Back test ZBI-22 HQ-CT in conjunction with the FSZQ After the first year of participation, changes from Baseline in: 		
	 ESS-CHAD as reported by caregivers/parents CaGI-S CGI-S for overall clinical status related to PWS 		
Safety	Safety Endpoints		
To assess the safety and tolerability of pitolisant in patient with PWS	 AEs Clinical laboratory results Vital signs 12-lead ECG Suicidality (C-SSRS) 		

Anxiety (ADAMS) Seizures Physical Examinations

Abbreviations: ABC-2 = Aberrant Behavior Checklist, Second Edition; ADAMS = Anxiety, Depression, and Mood Scale; AE = Adverse Event; C-SSRS = Columbia-Suicide Severity Rating Scale; CAGI-S = Caregiver Global Impression of Severity; CGI-S = Clinical Global Impression of Severity; ECG = electrocardiogram; EDS = Excessive Daytime Sleepiness; ESS-CHAD = Epworth Sleepiness Scale for Children and Adolescents; FSZQ = Food Safe Zone Questionnaire; HQ-CT = Hyperphagia Questionnaire for Clinical Trials; MERS-PWS = Montefiore-Einstein Rigidity Scale – Prader-Willi Syndrome; PWS = Prader-Willi Syndrome; ZBI-22 = 22-item Zarit Burden Interview.

9.2 Study Day Windows

For each patient there will be a Screening period, a Double-Blind Treatment Phase, and an OLE Phase (optional).

The study day for data collected prior to first dose, will be calculated as visit date – first dose date. For data collected after the first dose, the study day will be calculated as visit/assessment date – first dose date + 1. The first dose date refers to the date the study drug was taken for the first time, i.e., at the beginning of the Double-Blind Treatment Phase.

9.2.1 Visit Window

The visit window and PK draw window appear in Table 5 and Table 6, respectively. For the Double-Blind Treatment Phase, unless otherwise stated, the endpoints will be analyzed and reported using the analysis visits as determined by the windowing. For the OLE Phase, unless otherwise stated, the nominal visit will be used.

During the Double-Blind Treatment Phase, if a patient stopped taking treatment before their CRF Visit 3 (start of the stable dose) for a reason other than AE and then re-started study treatment more than 14 days after the treatment interruption, the analysis visit window for post-baseline visits will be derived using (as Day 1) the date the patient re-started their study treatment (i.e., the visit window will not be based on date of first dose for that patient).

Table 5: Visit Window and Target Day

Phase	Protocol Visit	Analysis Visit	Target Day	Visit Window Lower Limit	Visit Window Upper Limit
Safety: Vital Signs (including Height and Weight), Physical Examination, Clinical Laboratory, 12-lead ECG Efficacy: ESS-CHAD (parent/caregiver version), CaGI-S, CGI-S					
Screening	Visit 1 Visit 2	Baseline	-1	- inf	1
	Visit 3	Visit 3 (Day 22)	22	2	35
Daubla	Visit 4	Visit 4 (Day 50)	50	36	63
Double- Blind	Visit 5	Visit 5 (Day 77)	77	64	Treatment Phase Completion ^a
OLE	Visit 6	Visit 6 (Month 4)	99		-
	Visit 7	Visit 7 (Month 6)	189		

Dhasa	Protocol	Analysis Visit	Tayget Day	Visit Window	Visit Window
Phase	Visit		Target Day	Lower Limit	Upper Limit
	Visit 8	Visit 8 (Month 9)	279		
	Visit 9	Visit 9 (Month 12)	369		
Visit x		Visit x (Month y) ^b	Previous visit target day + 180		
Efficacy: G	hrelin meas	urements			
Screening	Visit 2	Baseline	-1	- inf	1
Double- Blind	Visit 5	Visit 5 (Day 77)	77	2	+ inf
Efficacy: C	ogstate		-		•
Screening	Visit 1	Baseline	-1	- inf	1
Screening	Visit 2	Dascinic		- 1111	
	Visit 4	Visit 4 (Day 50)	50	36	63
Double- Blind	Visit 5	Visit 5 (Day 77)	77	64	Treatment Phase Completion ^a
	Visit 6	Visit 6 (Month 4) ^c	99		
OL E	Visit 7	Visit 7 (Month 6)	189		
OLE	Visit 8	Visit 8 (Month 9)	279		
	Visit 9	Visit 9 (Month 12)	369		
Efficacy: A	BC-2, MER	S-PWS ^c , ZBI-22, HQ-0	CT and FSZQ		
Screening	Visit 1 Visit 2	Baseline	-1	- inf	1
	Visit 3	Visit 3 (Day 22)	22	2	35
	Visit 4	Visit 4 (Day 50)	50	36	63
Double- Blind	Visit 5	Visit 5 (Day 77)	77	64	Treatment Phase Completion
OLE	Visit 6	Visit 6 (Month 4)	99		
	Visit 7	Visit 7 (Month 6)	189		
OLE	Visit 8	Visit 8 (Month 9)	279		
	Visit 9	Visit 9 (Month 12)	369		
PK					
D11	Visit 3	Visit 3 (Day 22)	22	2	35
Double- Blind	Visit 4	Visit 4 (Day 50)	50	36	63

Abbreviations: ABC-2 = Aberrant Behavior Checklist, Second Edition; ADAMS = Anxiety, Depression, and Mood Scale; C-SSRS = Columbia-Suicide Severity Rating Scale; CAGI-S = Caregiver Global Impression of Severity; CGI-S = Clinical Global Impression of Severity; ECG = electrocardiogram; ESS-CHAD = Epworth Sleepiness Scale for Children and Adolescents; FSZQ = Food Safe Zone Questionnaire; HQ-CT = Hyperphagia Questionnaire for Clinical Trials; MERS-PWS = Montefiore-Einstein Rigidity Scale – Prader-Willi Syndrome; PWS = Prader-Willi Syndrome; ZBI-22 = 22-item Zarit Burden Interview.

Note: For MSLT, C-SSRS and ADAMS no analysis window will be applied; data will be reported using the nominal visit.

Table 6: PK Draw Timing

Visit	Target Day		
Visit 3	Day 22	Any time after the morning dose of the study drug	
Visit 4	Day 50	 Pre-dose Between 45 and 75 minutes after dosing, Between 1.5 and 2.5 hours after dosing, Between 3.0 and 4.0 hours after dosing, Between 5.0 and 6.0 hours after dosing 	
Visit 5	77	Any time after the morning dose of the study drug	

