3.1.6. Dose Interruptions

Every effort should be made to educate patients/caregivers/parent(s)/legal guardian(s) on the importance of remaining compliant with study drug dosing.

No interruptions in study drug dosing are expected in the Double-Blind Treatment Phase of the study. If a dose is missed in the Double-Blind Treatment Phase, the patient should take the next dose the following morning upon wakening. If dosing is interrupted (e.g., due to an AE) for 7 or more days, consult with the Medical Monitor before restarting study drug.

In the OLE Phase of the study, interruptions in study drug dosing are permitted based on tolerability and the discretion of the Investigator. If a dose is missed in the OLE Phase, the patient should take the next dose the following morning upon wakening.

If a patient is taking a pitolisant dose that is >8.9 mg and has a dosing interruption exceeding 7 days in the OLE Phase, before restarting study drug, the Investigator should consult with the Medical Monitor.

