7.3.2. Stable Dose Period, Double-Blind Treatment Phase (Days 22 to 77)

Patients will continue to take study drug at their randomized stable dose during the Stable Dose Period and will return with their caregivers to the study site on Day 22, Day 50, and Day 77 (±3 days; Visits 3, 4, and 5, respectively) for safety, efficacy, and PK assessments. Patients and/or their caregivers will be contacted by the study site by telephone on Days 29, 36, and 57 (±3 days; TCs 3, 4, and 5, respectively) to assess for AEs and concomitant medication use, complete the C-SSRS and ADAMS, and confirm compliance with study drug administration.

The last dose of blinded treatment is on Day 77 ± 3 days (Visit 5; EOT Visit in the Double-Blind Treatment Phase).

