Visit 5 (Day 77 ± 3 days) is the EOT visit in the Double-Blind Treatment Phase of the study. A fasting blood sample for ghrelin testing will be collected at this visit; therefore, the patient should fast on the night before Visit 5. The patient (with the assistance of their caregiver if necessary) should record in the study diary the time of study drug dosing on the morning of Day 77, Visit 5. The following evaluations will be performed at Visit 5:

- Urine pregnancy test (FCBP only)
- Urine drug screen
- Full physical examination
- Body weight and height
- Vital signs
- 12-lead ECG (in triplicate)
- C-SSRS (Appendix M)
- ADAMS
- Clinical laboratory tests (serum chemistry, hematology, urinalysis); may be collected with the fasting serum ghrelin measurement and the PK blood sample collection
- Serum ghrelin measurement (fasting)
- Blood sample collection for PK analyses (sample may be collected at the same time as clinical laboratory tests and fasting serum ghrelin measurement; time of last dose of study drug and time of blood sample collection for PK is to be recorded)
- Review of AEs

- Review of concomitant medications
- ESS-CHAD (parent/caregiver version)
- CaGI-S (for EDS)
- CGI-S (for overall clinical status related to PWS)
- ABC-C
- MERS-R-PWS
- Cogstate Detection Test
- Cogstate Identification Test
- Cogstate One Back Test
- ZBI-22
- HO-CT
- FSZQ
- Review study drug compliance/accountability (Section 5.5 and Section 5.6)

Patients will be given the opportunity to participate in the OLE Phase at this visit. Eligible patients who enter the optional OLE Phase will be dispensed open-label pitolisant (Section 5.2.2); eligibility criteria must be confirmed before patients receive open-label pitolisant. Patients will be instructed to begin taking open-label pitolisant on the following day in the morning upon wakening (Day 78 ± 3 days).

Patients who do not enter the OLE Phase will be receive Safety Follow-up TCs from the study site 15 days (\pm 3 days) and 30 days (\pm 3 days) after last dose of blinded treatment, as outlined in Section 7.5.

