9.2.2 Data Selection for Multiple Results

Double-Blind Treatment Phase: For post-baseline assessments, if there are multiple non-missing results within the same analysis windows (including scheduled and unscheduled results) the non-missing result that is the closest to the target date will be used in the analyses; if more than one result is equally close, the result that is after the target date for the assessment will be used. If necessary, time of the assessments (if collected) will be used to determine the record to be selected. If there is still more than one result to be selected (but with different results), the average will be derived and then selected for analysis.

OLE Phase: The assessments performed at the nominal visits will be used in the analyses/summaries. Unscheduled assessments will only be used to determine worst, lowest and/or highest results post-baseline (where applicable).

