Discontinued	Present	Present	Missing	Missing data after the discontinuation will be imputed within treatment group using MI approach with observed values at all available time points (including Baseline).	
due to any reason but lack of efficacy or	Present	Missing	Missing		
AE	Missing	Missing	Missing		

Abbreviations: AE = Adverse Event; MI = Multiple Imputation.

Note: Multiple imputation method is performed using the analysis visits, i.e., if the nominal result is missing, and there is an unscheduled result or if the ET result falls within the visit window that assessment will be used at that visit.

Step 1. Monotone Missing Pattern: Intermittent missing data will be imputed within treatment group using MI under a missing at random assumption with observed values at all available time points (including Baseline).

- a. From the analysis dataset containing the ESS-CHAD (parent/caregiver version) results, select all the patients (regardless of the discontinuation reason and status). The dataset will contain indicators variables for subject ID: SUBJID, planned treatment: TRTP, Baseline results: BASELINE, Visit 3 results: VISIT3, Visit 4 results: VISIT4 and Visit 5 results: VISIT5) and there will be one record per patient. Before transposing the dataset to get the required structure, if there are multiple non-missing records for a patient, select the record to include as per the rules defined in section 9.2.
- b. Using this dataset with treatment as covariate, imputed datasets (called imputations) will be produced using the Markov Chain Monte Carlo (MCMC) method implemented with the SAS MI procedure. The imputed datasets will contain the observed value (where it was not originally missing) or imputed values as per the model (for missing observations). The values imputed by MCMC method for the missing values will be used for patients who completed the treatment phase but have monotone patterns of missing data.

Step 2. Missing data for patients who discontinued for other reasons (i.e., not due to lack of efficacy or AE): Missing data after the treatment discontinuation (i.e., in the 'tail' end) will be imputed within treatment group distribution (intermittent missing data will have been imputed at the previous step). Patients who completed the treatment but have missing values not imputed at the previous step (i.e., at the 'tail' end) will have their missing imputed together with patients who discontinued for other reasons.

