12.4.1.3.2 Estimand

The primary efficacy endpoint is defined as the change in mean ESS-CHAD (parent/caregiver version) score from Baseline to Week 11 (Visit 5) for high dose pitolisant compared with placebo.

The target population is all patients in the mITT population with PWS as defined by the inclusion/exclusion criteria.

A treatment policy strategy will be used to address intercurrent events. No special data handling will be used for patients who initiate concomitant medications, have intermittent missing data, or discontinue study medication (even if they report data following discontinuation of study medication). No explicit imputation of missing data will be performed; the MMRM approach assumes data are missing at random and will provide unbiased results if this is the case. Sensitivity analyses will explore the results under different analysis assumptions.

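### SAP 9.2.1 restarts the visit clock after some dosing gaps without requiring that visits were re-timed; if visits stayed on schedule, an observed Week 11 ESS-CHAD is labelled as an earlier visit

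*SAP*

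**What the plan says.** In the Double-Blind Treatment Phase, endpoints are analysed by windowed visit (SAP 9.2.1, Table 5). For ESS-CHAD the windows are Days 2 to 35 for Visit 3, Days 36 to 63 for Visit 4, and Day 64 to completion of the phase for Visit 5. Days normally count from first dose. The exception covers patients who stopped before CRF Visit 3 for a non-AE reason and restarted more than 14 days later. For them, "the analysis visit window for post-baseline visits will be derived using (as Day 1) the date the patient re-started their study treatment". Where several results fall in one window, "the non-missing result that is the closest to the target date will be used in the analyses" (SAP 9.2.2).

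Protocol 7.3.2 has patients return "to the study site on Day 22, Day 50, and Day 77", each ±3 days. On gaps, Protocol 3.1.6 says "No interruptions in study drug dosing are expected in the Double-Blind Treatment Phase of the study". For a gap of 7 or more days it asks for consultation with the Medical Monitor before restarting. It does not say whether visits move.

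The primary comparison is high dose against placebo at Visit 5 (SAP 12.4.1.3.3), and the estimand section states that "A treatment policy strategy will be used to address intercurrent events" (SAP 12.4.1.3.2).

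**The concern.** The rule suits one pattern of visit timing and does not say that it assumes it. Following the protocol schedule and the SAP rule together, both as written, moves an end-of-treatment score taken on Day 77 out of the Week 11 window. The primary MMRM then uses that score as an earlier visit and treats Week 11 as missing, although it was recorded. In the multiple-imputation sensitivity analysis the patient falls under Step 2 ("Patients who completed the treatment but have missing values not imputed at the previous step"), so a value that exists would be imputed.

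A treatment-policy strategy is meant to use the outcome at the planned time whatever happened to treatment. Losing it because of a labelling rule runs against that aim.

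**Working it through.** **Inputs.** Windows and targets come from SAP Table 5. The day convention is SAP 9.2: date minus reference date plus 1 on or after the reference date, and date minus reference date before it. The schedule is Protocol 7.3.2. The trigger is SAP 9.2.1.

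**Table 5 reproduced.** The limits are midpoints between target days: (22 + 50)/2 = 36 gives the split 35|36, and (50 + 77)/2 = 63.5 gives 63|64. Both match.

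**Earliest restart.** A gap of more than 14 days that starts on Day 1 ends on Day 16 at the earliest (16 − 1 = 15).

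**When Day 77 stays in Visit 5.** With restart day r, the condition is 77 − r + 1 ≥ 64, so r ≤ 14. The trigger needs r ≥ 16, so a Day 77 score always leaves the window.

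| Restart day | Days 22 / 50 / 77 become | Day 77 score analysed as | Visit 5 |
|---|---|---|---|
| 16 | 7 / 35 / 62 | Visit 4 | missing |
| 20 | 3 / 31 / 58 | Visit 4 | missing |
| 28 | −6 / 23 / 50 | Visit 4 | missing |
| 42 | −20 / 9 / 36 | Visit 4 | missing |

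In each row the nominal Visit 4 score becomes analysis Visit 3. From a Day 43 restart, Day 77 falls in the Visit 3 window (77 − 43 + 1 = 35).

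**Visits off target by up to 3 days.** The end-of-treatment score stays in Visit 5 only if taken on Day 79 or 80 with a Day 16 restart (64 or 65), or on Day 80 with a Day 17 restart (64). With late restarts it can also go unused. For a Day 40 restart and visits on Days 22, 50 and 74, Day 74 becomes 35 (13 days from the Visit 3 target) and loses to Day 50, which becomes 11 (11 days from it).

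**Would another clock do better?** For a Day 16 restart, full re-timing adds 15 days to each visit. The last three columns give the record used for Visit 5.

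| Actual days of Visits 3 / 4 / 5 | Restart clock | First-dose clock | Nominal CRF label |
|---|---|---|---|
| 22 / 50 / 77 (on schedule) | none | Day 77 | Day 77 |
| 37 / 65 / 92 (all re-timed) | Day 92 | Day 65 | Day 92 |
| 37 / 50 / 77 (partly) | none | Day 77 | Day 77 |
| 22 / 65 / 92 (partly) | Day 92 | Day 65 | Day 92 |

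On the first-dose clock, Day 65 is 12 days from the Day 77 target and Day 92 is 15 days from it, so the wrong record wins. Neither clock is right in all four rows. The nominal label is.

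**Precision.** At SD 5 and 20 per arm (Protocol 9.2), the standard error of a pairwise difference is 5 × √(1/20 + 1/20) = 1.581. With one Week 11 value lost in one arm it is 5 × √(1/20 + 1/19) = 1.602 (+1.3%). With two lost it is 5 × √(1/20 + 1/18) = 1.624 (+2.7%). These are complete-case upper bounds, because the MMRM also uses the patient's other visits.

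**The case against.** The strongest reply is that the rule was written for patients whose visits moved, and trial mechanics support this. SAP 9.2.1 itself describes Visit 3 as the start of the stable dose. SAP 12.3.2.1 dates the stable-dose period from Visit 3. Stable-dose drug is dispensed at that visit, and its PK sample follows a morning dose (Protocol 7.3.2.1, SAP Table 6). A patient still off drug could not meet those requirements on Day 22. This stands as evidence of intent, and for such patients the rule works.

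It does not supply the missing condition. The protocol has no re-timing rule, and the SAP applies the restart clock whatever the visit dates were. Moving Visit 3 alone does not help either: with visits on Days 37, 50 and 77 after a Day 16 restart, Week 11 is still lost.

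It is also fair to say that the MMRM usually keeps the relabelled score, that the protocol expects no interruptions, and that this is a proof-of-concept trial without a strict significance objective. These points limit the weight of the finding but do not make the label right.

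**Conclusion.** The point holds as a minor one. It rests on two conditions: that some patient meets the trigger, and that this patient's Visit 5 stayed on the original calendar. Under those conditions a Day 77 score always leaves the Visit 5 window. The only escapes within ±3 days are Days 79 and 80 with a Day 16 restart, and Day 80 with a Day 17 restart.

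A reader might infer more than the documents support:

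- **That the rule is wrong for everyone it covers.** It is correct where all later visits were re-timed.
- **That a known share of Week 11 scores is lost, or that the treatment difference is biased.** The documents give neither the number of such gaps, nor their arm, nor how visits were timed. The number may be zero.
- **That the rule contradicts the estimand outright.** The sentence in SAP 12.4.1.3.2 ruling out special data handling does not name stopping and restarting, so poor fit is as far as the text goes. The same applies to the rule's separate treatment of AE gaps, which keep the first-dose clock. That is an explicit choice, and the finding does not depend on it.

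**What to change.** In SAP 9.2.1, for patients who meet the trigger, assign the scheduled CRF Visits 3, 4 and 5 to analysis visits by their nominal CRF label. This is correct whether visits were on schedule, re-timed or partly re-timed. Use the restart-based window only for unscheduled and early-termination records, and state that a scheduled record takes precedence where both fall in the same analysis visit. The SAP already reports some double-blind data by nominal visit: "For MSLT, C-SSRS and ADAMS no analysis window will be applied; data will be reported using the nominal visit".

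Apply the change before unblinding. Protocol 1.3.2 describes the Double-Blind Treatment Phase as completed, so if unblinding has already taken place, report the nominal-label result as a sensitivity analysis instead. In either case give the number of affected patients by arm.

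The cost is one or two sentences in the SAP, a flag, and one further run of the primary model only if the count is not zero. No new data are needed. The downside is that for re-timed patients the Week 11 record lies later than Day 77 from first dose: Day 92 (77 + 15) or later for on-target visits. Extending the same approach to AE gaps is optional.
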